Official Title: To Understand the Impact of Immunosuppression Using Once-perday Envarsus XR on the Effect of Total Tacrolimus Dose/Trough Level Ratio on Renal Function (eGFR) in Kidney Transplantation

Unique Protocol ID: AAAR6805

Registration Identifier: NCT03511560

Document Date: June 11, 2019

Primary Objective: To compare the relationship of once daily tacrolimus extended release (Envarsus) versus twice daily tacrolimus immediate release (Prograf) doses to achieve target trough concentrations (C) relative to the total daily dose (D) given and the effect of C/D ratio on renal function at day 7 and months 1, 3, 6, and 12 months after transplantation utilizing concentration to dose ratio (C/D ratio).

Secondary Objective:

- Compare incidence of rejection between the groups at 90 and 365 days post-transplant (Banff grade I-III and antibody mediated rejection [AMR])
- Compare graft loss and death within 1 year post-transplant
- Death within 1 year post-transplant
- Compare and summarize serious adverse events (AEs) between study groups

Study Population: Living or deceased donor kidney transplant recipients 18 to 80 years of age.

Number of Subjects to be Enrolled / Randomized: 50 patients [25 patients in each arm]

Study Design Overview:

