- 5. Previous kidney transplants will be permitted. Patients who are receiving a secondary transplant and who previously received Envarsus or who are currently on Envarsus as a component of maintenance immunosuppression and re-listed for transplant will be eligible to enroll in this study and will be randomized at the time of transplant to either cohort.
- 6. Subject agrees not to participate in another study while on treatment.
- 7. Female subject must be either:
 - a. Of non-child-bearing potential,
 - i. Post-menopausal (defined as at least 1 year without any menses) prior to screening, or
 - ii. Documented surgically sterile or status post-hysterectomy
 - b. Or, if of childbearing potential,
 - i. Agree not to try to become pregnant during the study and for 90 days after the final study drug administration
 - ii. And have a negative serum or urine pregnancy test within 14 days prior to transplant procedure
 - iii. And, if heterosexually active, agree to consistently use two forms of highly effective birth control (at least one of which must be a barrier method) which includes consistent and correct usage of established oral contraception, established intrauterine device or intrauterine system, or barrier methods of contraception: condom or occlusive cap (diaphragm or cervical/vault caps) with spermicidal foam/gel/film/cream/suppository, starting at screening and throughout the study period and for 90 days after the final study drug administration.
- 8. Male subject and their female spouse/partners who are of childbearing potential must be using highly effective contraception consisting of two forms of birth control (one of which must be a barrier method) starting at screening and continuing throughout the study period and for 90 days after the final study drug administration).
- 9. Female subjects must agree to not breastfeed from screening through end of the study period.

Waivers to the inclusion criteria will NOT be allowed. Patients meeting inclusion criteria at the time of randomization and not initiated on Envarsus or immediate-release tacrolimus within 48 hours of transplant will be classified as a recruitment failure and not included in the analysis.

Exclusion Criteria:

Subject will be excluded from participation if any of the following apply:

- 1. Patient is known to have a positive test for latent tuberculosis (TB) and has not previously received adequate anti-microbial therapy or would require TB prophylaxis after transplant.

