All patients will receive induction immunotherapy (either T-cell depleting agent or IL-2 co-stimulation blocker). The dose and frequency of the chosen induction agent will be determined by the patient's treating physician and administered in conjunction with the participating transplant center's *de novo* kidney immunosuppression protocol. As a participant in this study, in addition to tacrolimus, study subjects will need to concomitantly receive mycophenolate sodium (or MMF equivalent). Anti-CMV, fungal, bacterial, and pneumocystis prophylaxis will follow standard of care. Non-tacrolimus based immunosuppressive regimens (i.e. cyclosporine, everolimus, sirolimus, belatacept), as well as all forms of extended-release tacrolimus other than Envarsus, are prohibited during the course of the study. *Measures to Treat Rejections:* The need for therapy to treat rejection will be determined by the supervising physician. Typical rescue drugs employed under these conditions include, but are not limited to rabbit anti-thymocyte globulin, intravenous immunoglobulin (IVIG), rituximab, and eculizumab.

Duration of Treatment:

Study enrollees will receive study medication (single daily dose of Envarsus or standard of care twice daily, immediaterelease tacrolimus) for up to one year following their transplant procedure.

Formal Stopping Rules:

A decision to terminate the study early will be based on the event rate of rejections or AE's as determined by the Research Committee of the Renal Transplantation Service comprised of all nephrologists, surgeons, and transplant coordinators which meets monthly. The study duration will be such that patients will complete at least one year of study visits. Interim data analysis will be performed once all patients complete 6 months of study and final analysis will be performed when all patients complete 12 months of study.

Discontinuation Criteria from Treatment for Individual Subjects:

Subject develops allograft loss (as defined by subject death, re-transplantation, transplant nephrectomy, or return to dialysis of \geq 6 consecutive weeks);

Subject develops unacceptable toxicity or is withdrawn at the discretion of the patient's supervising physician; Subject is lost to follow-up despite reasonable efforts by the investigator to locate the subject;

Subject withdraws consent for further treatment;

Conversion to a non-tacrolimus-based maintenance regimen in either study arm if required to manage toxicities.

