Endpoints for Evaluation:

Primary: To compare the relationship of once daily tacrolimus extended release (Envarsus) versus twice daily tacrolimus immediate release (Prograf) doses to achieve target trough concentrations (C) relative to the total daily dose (D) given

and the effect of C/D ratio on renal function at day 7 and months 1, 3, 6, and 12 months after transplantation utilizing concentration to dose ratio (C/D ratio).

Secondary: Comparison between treatment cohorts regarding incidence will rely upon assessments for each of the following results:

- Compare incidence of rejection between the groups at 90 and 365 days post-transplant (Banff grade I-III and antibody mediated rejection [AMR])
- Compare graft loss and death within 1 year post-transplant
- Compare and summarize serious adverse events (AEs) between study groups
- Death within 1 year post-transplant

Statistical Analysis:

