Sample Size: The sample size for this pilot study is not sufficiently powered to document that the C/D ratio in each patient group will correlate directly with eGFR. We expect to see a trend suggestive that the Envarsus group by virtue of more stable Tacrolimus level and greater compliance over time will be less likely to develop calcineurin-induced nephrotoxicity and therefore result in a better e-GFR. This is not likely to be statistically significant in this inadequately powered study since the variability in donor organs themselves, as well as many other variables, will not permit a precise analysis in this small study sample. However, stratification for living donors and deceased donors may provide important trends in this pilot project which may then guide us to expand the study in more restricted categories of renal allograft recipients. The statistical summary and analysis of safety data, will consist of all subjects who enrolled into the study and took at least one dose of study medication. Demographics and other baseline characteristics will be summarized by treatment group. Descriptive statistics (e.g., n, mean, standard deviation, minimum, median, maximum) and interquartile range, coefficient of variation, and geometric mean will be provided for tacrolimus dose and whole blood concentrations of tacrolimus for both study cohorts. Tacrolimus concentrations will be summarized with descriptive statistics. The analysis of efficacy regarding C/D effectiveness in relation to number of rejection episodes and outcomes at various stated time points will be conducted using Student T test. The association between whole blood concentrations and the following endpoints will be assessed: rejection episode and eGFR, histopathology (Banff classification) and conventional measures of transplant outcomes.

H0: The probability of incidence for the primary endpoint is the same between patients receiving Envarsus and patients receiving immediate-release tacrolimus.

Safety: All adverse events (AE) will be listed. The number and percentage of AEs, significant AEs, AEs leading to discontinuation, and AEs related to study drug will be summarized by treatment group. The number and percentage of AEs by severity will also be summarized.

Randomization will be performed in excel prior to initiation: Allocation will consist of a 1:1 ratio for twice daily, immediate-release tacrolimus or Envarsus.

Institutional Review Board (IRB)

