Medical History: Etiology of renal failure, viral serology (HBV, HCV, CMV, EBV), and diabetes history (as applicable). *Transplant Information*: Day 0 visit: type of transplant (living related, living non-related, DD, and whether organ was obtained in the setting of DCD or CDC), number of prior transplants and reason for prior graft loss (if applicable), total cold and warm ischemia time in hours and minutes, KDPI, ABO blood typing, HLA typing of donor and recipient, degree of HLA mismatch between donor and recipient, and most recent panel reactive antibody testing. Donor viral serology information (HBV, HCV, CMV, EBV), if available, will be collected and recorded. Additional donor information includes age, sex, height, weight, donor cause of death, ethnicity, ABO typing, and results of any pre-implantation biopsies. *Height and Body Weight*: Height and dry weight will be recorded at screening and pre-operatively on study day 0.

Efficacy Assessment

Estimated Glomerular Filtration Rate: Estimated glomerular filtration rate (eGFR) will be calculated at day 7 and months 1, 3, 6, and 12 using the Modification of Diet in Renal Disease (4 variable – MDRD) criteria.

Calculation of C/D Ratio: Calculation of the daily trough level over the average daily total tacrolimus dose delivered either by ENVARSUS or by SOC twice a day Tacrolimus will be performed monthly throughout the study.

Patient Survival: Patient survival is any subject that is known to be alive at the study conclusion.

Graft Survival: Graft survival is defined as any subject that does not fit the following definition of graft loss: subject death, re-transplantation, transplant nephrectomy, or return to dialysis for a period of ≥6 weeks by study end. *Acute Rejection*: For study purposes, diagnoses of rejection require biopsy confirmation. Both acute cellular and antibody mediated rejection will be assessed and graded according to published criteria [Solez et al, 2008] by the NYPH

Renal Pathology Division pathologist.

Adverse Events

Adverse event collection will begin once informed consent has been signed and continue throughout the subject's participation in the study. A subset of the routine laboratory assessments obtained per SOC, including creatinine, hemoglobin, hematocrit; platelet count; white blood cell count; serum sodium, potassium, blood urea nitrogen, glucose, urinalysis (including urinary protein), tacrolimus trough concentrations.

Physical Examination

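### The patient-survival and graft-survival definitions class a patient of unknown status in opposite ways, so reported graft survival could exceed patient survival

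*Combined protocol and SAP*

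**What the plan says.** The Efficacy Assessment section of the combined protocol and SAP gives two definitions. The one for patients rests on what is known at the end: "Patient survival is any subject that is known to be alive at the study conclusion".

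The one for the graft works the other way round and rests on a list of loss events, of which death is the first: "Graft survival is defined as any subject that does not fit the following definition of graft loss: subject death, re-transplantation, transplant nephrectomy". The list closes with dialysis that has been resumed and has lasted at least six weeks when the study ends.

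The outcomes to be compared are listed elsewhere, and as events. The Secondary Objective and the Endpoints for Evaluation both include "Compare graft loss and death within 1 year post-transplant", and both list death separately. The Study Design Overview also names graft loss and patient death as one-year outcomes. The Endpoints section introduces its secondary list with "Comparison between treatment cohorts regarding incidence will rely upon assessments for each of the following results".

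Loss to follow-up is foreseen. Both statements of the individual discontinuation criteria include "Subject is lost to follow-up despite reasonable efforts by the investigator to locate the subject". No section says how such a patient is classed for death or graft loss. The Statistical Analysis section names no censoring or time-to-event method for either outcome.

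**The concern.** The two definitions place the burden of proof on opposite sides. A patient must be shown to be alive to count as a survivor, whereas a graft survives unless a loss is shown. For a patient whose status is unknown and who has no recorded event, the first rule returns failure and the second returns success.

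Because death is itself a graft loss, true graft survival can never be higher than true patient survival. A table built from these definitions could show the reverse. If the number of unknown patients differed between arms, patient survival would also show a difference that no recorded death explains. These are the hard outcomes that a reader of a transplant trial looks for, so the classification should not be left to be settled after the data are seen.

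**Working it through.** **Inputs.** The plan states no survival, graft-loss or dropout figure, so there is nothing to reproduce beyond 2 x 25 = 50 patients.

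- N = analysed patients per arm. Planned enrolment is 25 per arm; that all 25 are analysed is an assumption.
- L = patients of unknown status with no recorded event. Assumed 0 to 3 per arm.
- D = recorded deaths; G = graft losses other than death, with vital status known. Both are illustrative.

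**Formulas.**

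- Survival definitions applied literally to recorded data: patient (N - D - L)/N; graft (N - D - G)/N.
- Recorded events counted: patient (N - D)/N; graft (N - D - G)/N.
- Unknown treated as missing for both: patient (N - L - D)/(N - L); graft (N - L - D - G)/(N - L).

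With G = 0, the first pair differs by L/N in favour of graft survival. Each unknown patient therefore adds 100/N points: 4.0 at N = 25 and 5.0 at N = 20.

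**Results at N = 25, patient vs graft survival.**

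| D | G | L | Definitions as written | Recorded events | Unknown as missing |
|---|---|---|---|---|---|
| 0 | 0 | 0 | 100% vs 100% | 100% vs 100% | 100% vs 100% |
| 0 | 0 | 1 | 24/25 = 96% vs 100% | 100% vs 100% | 100% vs 100% |
| 0 | 0 | 2 | 23/25 = 92% vs 100% | 100% vs 100% | 100% vs 100% |
| 0 | 0 | 3 | 22/25 = 88% vs 100% | 100% vs 100% | 100% vs 100% |
| 1 | 0 | 3 | 21/25 = 84% vs 24/25 = 96% | 96% vs 96% | 21/22 = 95.5% vs 95.5% |
| 0 | 1 | 2 | 23/25 = 92% vs 24/25 = 96% | 100% vs 96% | 23/23 = 100% vs 22/23 = 95.7% |

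The reversed order appears only in the column for the definitions as written, and only when L is above zero.

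**Unequal loss between arms.** With 3 unknown in one arm, none in the other and no deaths, patient survival as defined is 88% vs 100%. The two-sided Fisher exact p is 2 x C(25,3)/C(50,3) = 2 x 2,300/19,600 = 0.23. Counting recorded events, or treating unknown as missing, gives 100% in both arms.

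**Limit of the Kaplan-Meier remedy.** Suppose one of 25 patients loses the graft at day 60 and dies at day 300, and three others are lost between those days. Graft survival is 24/25 = 96% and patient survival is 1 - 1/22 = 95.5%. Common censoring removes the opposite handling of unknown status but does not guarantee the order of the two estimates in every data set.

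**The case against.** The strongest reply is that the survival definitions may never be tabulated. The objectives, the design overview and the endpoint list all name graft loss and death, and no endpoint list contains patient survival or graft survival as such. If recorded events are counted, unknown status is treated alike for both outcomes and the conflict disappears. This largely stands. A reader might infer that the plan leaves open whether events or survival rates are the endpoints, but the documents do not support that.

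A reader might also take the word for assessments in the endpoint list as a pointer to the Efficacy Assessment section. In full, the sentence points to the list that follows it.

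What remains is narrower. The Efficacy Assessment section is the only place where graft loss is defined as an outcome; the discontinuation criteria define it as a reason to stop treatment. Nothing says how its definitions feed the endpoints, so death could be read as a recorded death or as the complement of being known alive.

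A second reply is that the graft definition does not expressly class unknown status as survival. That is correct: the result assumes that the loss definition is judged on recorded data. The text offers no other rule.

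Third, unknown status may be rare. The Follow Ups section plans the same monthly contact in both arms, with a telephone call when a visit is missed. This lowers the likely size but does not supply a rule.

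Two further inferences would go too far.

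- **Time point.** The references to the end of the study need not mean a different time point. Final analysis is set at 12 months for all patients, and the Study Design section places the terminal visit at 12 months, so this is mostly a matter of wording.
- **Denominator.** The plan removes patients not started on tacrolimus within 48 hours ("will be classified as a recruitment failure and not included in the analysis") and defines a population only for the "analysis of safety data, will consist of all subjects who enrolled into the study and took at least one dose of study medication". Which patients form the denominator is a separate question and does not carry this point.

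**Conclusion.** The point holds in a limited form. Applied literally to recorded data, the two definitions make a patient of unknown status a non-survivor with a surviving graft. The gap is 4 percentage points per such patient at an assumed 25 per arm. One death and three unknown would be reported as 84% patient survival against 96% graft survival.

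These figures rest on assumed numbers of unknown patients. The effect is zero if every status is known or if recorded events are what is counted. A reader might infer that the plan would produce a false treatment difference, but the documents do not support that: nothing suggests unequal loss, and even 3 unknown against none gives p = 0.23.

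The severity is minor. Only secondary outcomes are affected, in a pilot that the Statistical Analysis section itself calls inadequately powered. The C/D ratio and eGFR analyses are untouched.

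**What to change.** - Replace the two survival definitions with the endpoints already listed: death, and all-cause graft loss including death, each within one year of transplant. State that the secondary comparison uses them.
- Apply one rule for unknown status to both outcomes. Either censor at last known status and report Kaplan-Meier one-year estimates, or, more simply, treat unknown as missing for both and state the denominator. Either is preferable to counting lost patients as event-free.
- Report the number of unknown status per arm. With Kaplan-Meier this also helps to explain any residual reversal of the kind shown in the working.
- Align the references to the end of the study with the 12-month time point.
- Reconcile the dialysis wording. The graft-survival definition requires six weeks or more by the end of the study, while the discontinuation criteria require the weeks to be consecutive. State how dialysis begun too late to reach six weeks is classified.

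The cost is a few sentences and minor analysis work, with no new visits, data or patients.

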This is a one year, prospective, randomized, open-label trial examining once versus twice daily tacrolimus dosing regimen using two preparations, Envarsus vs Prograf. It will examine kidney function between the two groups using eGFR and also examine one year kidney outcomes, including graft loss and patient death. Biopsy will be performed on clinical indications only (not protocol) when rejection or other problem is suspected in face of deteriorating renal function in each study group utilizing Banff criteria. Patients will be screened prior to surgery and randomized 1:1 to receive, within 48 hours of transplantation, immediate release tacrolimus, administered twice daily, or Envarsus, administered once daily as a component of a standard immunosuppression maintenance regimen also consisting of mycophenolate sodium (MPA) (or mycophenolate mofetil equivalent). Induction therapy will be given and administered per center protocol (rabbit anti-thymocyte globulin 6mg/kg over 4 days except in HLA identical living donor/recipient pairs when basiliximab induction is used intraoperatively). Intravenous corticosteroids (methylprednisolone 500mg intraoperatively with a daily rapid taper to 250, 125, 80 mg) over 4 days will be administered prior to rabbit antithymocyte globulin and prior to revascularization as part of the initial induction regimen. Thereafter, patients will be followed for up to 1 year during the open label study period. After discharge from the hospital, the patients randomized to immediate-release tacrolimus will be permitted to receive any immediate release tacrolimus product available to them through normal dispensing mechanisms. Envarsus will be supplied by Veloxis and dispensed by the research pharmacy.

Inclusion Criteria:

Subject is eligible for the study if all of the following apply:

1. Kidney transplant patient \ge 18 years and \le 80 years old

- 2. Institutional Review Board (IRB) approved written Informed Consent and privacy language must be obtained from the subject prior to any study-related procedures (including withdrawal of prohibited medication, if applicable).
- 3. Recipient of a *de novo* kidney from a living or deceased donor.
 - a. If deceased donor, a Kidney Donor Profile Index (KDPI) ≤ 85% are eligible for enrollment.
- 4. Willingness to comply with study protocol.

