This is an exploratory, pilot one year, prospective, randomized, open-label trial examining long-term kidney transplant outcomes. Specifically, it is designed to compare the effects of twice daily, immediate-release tacrolimus and once daily Envarsus on trough Tacrolimus concentrations (C) relative to the total daily dose (D) given and to determine the effect of C/D ratio on renal function at day 7 and months 1, 3, 6, and 12 months after transplantation utilizing concentration to dose ratio (C/D ratio). Patients will be screened prior to surgery and randomized 1:1 to receive, within 48 hours of transplantation, immediate-release tacrolimus, administered twice daily, or Envarsus once daily, as a component of a standard immunosuppression maintenance regimen also consisting of peri-transplant only corticosteroids and mycophenolate sodium (MPA), or equivalent. Induction therapy will be given and administered per center protocol. Intravenous corticosteroids will be administered prior to revascularization as part of the initial induction regimen, with dose and duration of therapy also determined by the standard protocol which tapers steroids off within 5 days of transplantation with few exceptions (patients who have been maintained on steroids prior to transplant and patients with IGA nephropathy). Thereafter, patients will be followed for up to 1 year during the open-label study period. Immediaterelease tacrolimus will be obtained from pharmacies per the local standard of care. After discharge from the hospital, the patients randomized to immediate-release tacrolimus will be permitted to receive any immediate-release tacrolimus product available to them through normal dispensing mechanisms. Envarsus will be supplied by Veloxis and dispensed by the Research Pharmacy. Additionally, all local kidney biopsy results, local laboratory results, AEs, and concomitant medications pertaining to AEs will be recorded. At the terminal study visit at 12 months, the most recently obtained lab results as well as any episodes of rejection, graft loss, and deaths occurring beyond the first year will be detailed and reported to the IRB. Pathology results [hematoxylin and eosin (H&E), light microscopy, and immunofluorescence] will be recorded when local kidney biopsies are performed and interpreted during the course of clinical care. Substantiation by local biopsy will be required for cases of suspected rejection. A kidney biopsy will be graded by the most recent version of the 2007 Update to the Banff '97 Classification by our renal pathologist blinded to clinical results.

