All AEs occurring during the study are to be followed up until resolved or judged to be no longer clinically significant, or until they become chronic to the extent that they can be fully characterized. If during AE follow-up, the adverse event progresses to an "SAE", or if a subject experiences a new SAE, the investigator must immediately report the information to the Sponsor. Local IRB will inform the investigator that some events reported as SAEs may not require expedited reporting to the IRB. The Sponsor will monitor these events throughout the course of the study.

Version Date: 11Jun2019 13 of 16

Procedure in Case of Pregnancy

If a female subject or partner of a male subject becomes pregnant during the study dosing period or within 30 days from the discontinuation of dosing, the investigator should report the information as an SAE. The expected date of delivery or expected date of the end of the pregnancy, last menstruation, estimated conception date, pregnancy result and neonatal data etc., should be included in this information. The medical status of the mother, as well as the fetus, will be followed and outcome reported to the IRB.

DISCONTINUATION

Discontinuation is defined as a subject who enrolled in the study and for whom study treatment is permanently discontinued prematurely for any reason. The subject is free to withdraw from the study treatment and/or study for any reason and at any time without giving reason for doing so and without penalty or prejudice. The investigator is also free to terminate a subject's involvement in the study at any time if the subject's clinical condition warrants.

Discontinuation Criteria from Treatment for Individual Subjects:

- Subject develops allograft loss (death, re-transplantation, transplant nephrectomy, or return to dialysis ≥ 6 consecutive weeks);
- Subject develops unacceptable toxicity or is withdrawn at the discretion of the patient's supervising physician;
- Subject is lost to follow-up despite reasonable efforts by the investigator to locate the subject;
- Subject withdraws consent for further treatment or expires during the course of the study;
- Conversion to a non-tacrolimus-based maintenance regimen in either study arm if required to manage toxicities;

OPERATIONAL AND ADMINISTRATIVE CONSIDERATIONS

Data Collection

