A protocol deviation is generally an unplanned excursion from the protocol that is not implemented or intended as a systematic change. The investigator is responsible for ensuring the study is conducted in accordance with the procedures and evaluations described in this protocol and for protecting the rights, safety, and welfare of subjects. The investigator should not implement any deviation from, or changes to, the protocol, unless it is necessary to eliminate an immediate hazard to trial subjects. For the purposes of this protocol, deviations requiring notification to Sponsor and to the local IRB are defined as any subject who: • Entered into the study even though they did not satisfy entry criteria. • Received wrong treatment or incorrect dose. • Received excluded concomitant treatment. When a deviation from the protocol is identified, the investigator or designee must ensure that local IRB is notified.

Documents and Records Related to the Clinical Study

The investigator will archive all study data in the patient's electronic data chart (e.g., Subject Identification Code List, source data, and eGFR,) and relevant correspondence. Data generated by the methods described in the protocol will be recorded in the subjects' medical records and/or study progress notes.

Protocol Amendment and/or Revision

Any changes to the study that arise after approval of the protocol must be documented as protocol amendments. Depending on the nature of the amendment, either IRB approval or notification may be required. The changes will become effective only after the approval of Veloxis, the investigator, and the IRB. Amendments to this protocol must be signed by Veloxis and the investigator. Written verification of IRB approval will be obtained before any amendment is implemented which affects subject safety or the evaluation of safety, and/or efficacy. Modifications to the protocol that are administrative in nature do not require IRB, but will be submitted to the IRB for their information. If there are changes to the Informed Consent, written verification of IRB approval must be forwarded to Veloxis. An approved copy of the new Informed Consent must also be forwarded to Veloxis.

Schedule of Events

	Screening (-21 to Day 0)	Randomization	Transplant (Day 0)	Month 1 - Month $12 (\pm 2 \text{ weeks})^3$
Consent	Х			
Demographic	Х			
Medical History	Х			Х
Height and weight ¹	Х		Х	Х
Transplant information			Х	
Randomization Assignment ²		Х		
IP Dispensation			Х	Х

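### Return to dialysis counts as graft loss only if 6 weeks are completed by an undefined study end, so permanent dialysis starting in about the last 6 weeks of the year can be classed as graft survival

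*Combined protocol and SAP*

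**What the plan says.** Four parts of the combined protocol and SAP bear on this point.

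- **Endpoint.** The secondary endpoints (Endpoints for Evaluation) include "Compare graft loss and death within 1 year post-transplant".
- **Definition.** Under Efficacy Assessment, "Graft survival is defined as any subject that does not fit the following definition of graft loss". The listed routes are "subject death, re-transplantation, transplant nephrectomy", none with a duration rule, and "return to dialysis for a period of ≥6 weeks by study end".
- **Follow-up.** Study Design Overview states that "patients will be followed for up to 1 year during the open label study period". Study Design calls the 12-month visit the terminal one. The Schedule of Events gives the monthly visits a window of plus or minus 2 weeks. Formal Stopping Rules places the final analysis at the point when all patients have completed 12 months.
- **A second version of the dialysis rule.** The individual discontinuation criteria, in the synopsis and again in the Discontinuation section, use "return to dialysis ≥ 6 consecutive weeks" or near-identical wording. They require consecutive weeks and have no study-end limit. The endpoint definition has the limit but does not say consecutive.

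No section defines study end, dates the loss to the start of dialysis, or lets the 6 weeks be confirmed after study end.

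**The concern.** The endpoint asks whether the graft was lost within 1 year. The definition asks whether 6 weeks of dialysis were completed by study end. These are different questions for a patient whose permanent dialysis starts late in the year. Graft survival is the default class, so such a patient is scored as a survivor and not as undetermined.

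At stake is the 1-year graft survival reported for each arm. With 25 patients per arm and few losses likely, one reclassified patient is 1/25 = 4 percentage points. The sample-size text says that trends from this pilot may guide an expanded study, so the descriptive rates may be carried forward.

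The visit window raises a related, smaller point. A Month 12 visit held 2 weeks early, at about day 351, is within the plan. It comes before the close of the 365-day rejection endpoint and of the 1-year graft-loss and death endpoints, and no later study visit is scheduled.

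**Working it through.** The documents give no graft-loss rate, power or event figure for this endpoint, so there is no stated number to reproduce. The check is date arithmetic followed by an illustrative size.

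**Inputs from the documents:** 6 weeks (42 days) of dialysis required; endpoint horizon of 1 year (day 365); visit window of plus or minus 2 weeks (14 days); 50 patients, 25 per arm.

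**Step 1. Study end read as the patient's Month 12 visit.** Latest dialysis start that can count = visit day − 42. Uncounted part of the year = 365 − that day.

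| Month 12 visit | Latest start that counts | Uncounted days | Share of year |
|---|---|---|---|
| day 351 | 351 − 42 = day 309 | 56 (8 weeks) | 56/365 = 15.3% |
| day 365 | 365 − 42 = day 323 | 42 (6 weeks) | 42/365 = 11.5% |
| day 379 | 379 − 42 = day 337 | 28 (4 weeks) | 28/365 = 7.7% |

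Example: dialysis starting on day 330 reaches 6 weeks on day 330 + 42 = 372. The patient is a graft loss if the visit falls on days 372 to 379, and a survivor if it falls on days 351 to 371. The class depends on the appointment date.

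**Step 2. Study end read as the end of the whole trial.** Early enrollees have time after their own day 365 to complete 6 weeks; the last enrollees do not. The definition would also no longer stop at day 365, so for early enrollees a return to dialysis starting after the first year could be counted. This reading does not give a uniform 1-year endpoint either.

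**Step 3. Size under the first reading.** Assumptions, not taken from the documents: a 1-year return-to-dialysis rate r of 2%, 5% or 10%, spread evenly over the year. With w the uncounted share of the year:

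Expected misclassified = 50 × r × w

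P(at least one) = 1 − (1 − r × w)^50

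At the nominal 6 weeks (w = 0.115):

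| r | Expected misclassified | P(at least one) |
|---|---|---|
| 2% | 50 × 0.02 × 0.115 = 0.12 | 11% |
| 5% | 50 × 0.05 × 0.115 = 0.29 | 25% |
| 10% | 50 × 0.10 × 0.115 = 0.58 | 44% |

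Extremes across the window: 50 × 0.02 × 0.077 = 0.08 (2%, every visit 2 weeks late) and 50 × 0.10 × 0.153 = 0.77 (10%, every visit 2 weeks early).

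**The case against.** The strongest reply is that study end is undefined, so misclassification is not proven. If it means the end of the trial, the gap shrinks to the last patients enrolled. That stands as a limit on certainty. It does not rescue the definition, because that reading gives patients unequal time and no stop at day 365. The follow-up and terminal-visit wording favours the Month 12 reading without settling it.

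The second reply is that the information would largely exist. Visits run alongside routine care, the hospital's electronic medical record (EMR) is the data source, serious events are reported within 24 hours of awareness, and adverse events are followed until resolved or fully characterized. This also stands. A reader might infer that late losses would go unrecorded; the documents do not support that. The gap is mainly one of classification, since none of these routes is tied to the endpoint rule.

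Third, the effect is small. The expected number is below one patient, the endpoint is secondary, and the plan itself says that the pilot is inadequately powered. All of this is correct.

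A reader might also infer that the 12-month visit cannot do what Study Design asks, namely that "any episodes of rejection, graft loss, and deaths occurring beyond the first year will be detailed and reported to the IRB". That goes too far: a visit on days 366 to 379 is within the window and can record such events. Only a visit on or before day 365 cannot.

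**Conclusion.** The point holds as a defect in the endpoint rule. Under the reading that the follow-up text favours, permanent dialysis starting in about the last 6 weeks of the year (4 to 8 weeks, 7.7% to 15.3% of the year) is classed as graft survival. Under the other reading, the endpoint is not a uniform 1-year endpoint.

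Three stronger conclusions are not supported:

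- That every graft failing late in the year is missed. Only the dialysis route is affected; the other three count at once.
- That 1-year graft survival will be overstated. It may be: the expected number at the nominal 6 weeks is 0.12 to 0.58 of 50 patients, and this rests on assumed rates and an even spread over the year. If returns to dialysis cluster early, it is lower.
- That the comparison of arms is biased. The same rule applies to both arms, and nothing in the documents shows a direction.

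The change is worth making because it is cheap and one patient moves an arm's rate by 4 points. It is not a threat to the primary objective.

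**What to change.** For the endpoint definition only:

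1. Remove the study-end limit from the dialysis component. Date graft loss to the first dialysis session of the episode. Count it as within 1 year if that session is on or before day 365 and dialysis then lasts at least 6 weeks, confirmed from the EMR after day 365 where needed.
2. Where the Month 12 visit falls before day 365, close the rejection, graft-loss and death endpoints with an EMR check on or after day 365.
3. Reconcile the dialysis wording in Efficacy Assessment with the consecutive-weeks wording in the discontinuation criteria, so that any intended difference is stated. This point takes no position on the discontinuation rule itself.

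The cost is a few sentences and one chart check for each patient concerned, using records that are already the data source. For a patient on dialysis at day 365, the data cut moves by up to 6 weeks.
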